5.5 Concomitant Therapy

The patient must be told to notify the investigational site about any new medications he/she takes after the start of the study drug. All medications (other than study drug) and significant non-drug therapies (including blood transfusions) administered during the study should be recorded.

If there is a clinical indication for one of these or other medications or vaccinations specifically prohibited during the trial, discontinuation from trial therapy or vaccination may be required

5.5.1 Acceptable Concomitant Medications

All treatments that the investigator considers necessary for a subject's welfare may be administered at the discretion of the investigator in keeping with the community standards of medical care. All concomitant medication will be recorded in the medical record including all prescription, over-the-counter (OTC), herbal supplements, and IV medications and fluids. If changes occur during the trial period, documentation of drug dosage, frequency, route, and date may also be included in the medical record.

All concomitant medications received within 28 days before the first dose of trial treatment and 30 days after the last dose of trial treatment should be recorded. Concomitant medications administered after 30 days after the last dose of trial treatment should be recorded for SAEs and ECIs as defined in Section 7.3.3.2.

5.5.2 Prohibited Concomitant Therapy

Subjects are prohibited from receiving the following therapies during the Screening and Treatment Phase (including retreatment for post-complete response relapse) of this trial:

- Antineoplastic systemic chemotherapy or biological therapy
- Immunotherapy not specified in this protocol
- Chemotherapy not specified in this protocol
- Investigational agents other than pembrolizumab
- Radiation therapy not specified in this protocol
- Note: Palliative radiation therapy for symptomatic but not progressing lesions may be allowed at the investigator's discretion so long as untreated target lesions remain for response assessment.
- Live vaccines within 30 days prior to the first dose of trial treatment and while participating in the trial. Examples of live vaccines include, but are not limited to, the following: measles, mumps, rubella, varicella/zoster, yellow fever, rabies, BCG, and typhoid vaccine.
- Systemic glucocorticoids for any purpose other than to modulate symptoms from an event of clinical interest of suspected immunologic etiology. The use of physiologic doses of corticosteroids may be approved after consultation with the Sponsor.

Subjects who, in the assessment by the investigator, require the use of any of the aforementioned treatments for clinical management should be removed from the trial. Subjects may receive other medications that the investigator deems to be medically necessary.

The Exclusion Criteria describes other medications which are prohibited in this trial.

There are no prohibited therapies during the Post-Treatment Follow-up Phase.

In addition, all patients (including those who discontinue the study early) should not receive other immunostimulatory agents (e.g., cytokines) for 10 weeks after the last dose of IL-2 with the exception of checkpoint blockade.

5.6 Rescue Medication & Supportive Care

5.6.1 Supportive Care for Radiotherapy

Radiotherapy is delivered as a standard of care palliative regimen and radiotherapy related toxicities will be addressed using standard institutional practices. With palliative doses delivered in this trial we anticipate minimal adverse effects for the treatment of dermal, subcutaneous, nodal, or visceral lesions.

Table 10 below shows treatment guidelines for subjects who experience an infusion reaction associated with administration of pembrolizumab (MK-3475).

Table 10. Infusion Reaction Treatment Guidelines

NCI CTCAE Grade	Treatment	Premedication at subsequent dosing
Grade 1 Mild reaction; infusion interruption not indicated; intervention not indicated	Increase monitoring of vital signs as medically indicated until the subject is deemed medically stable in the opinion of the investigator.	None
Grade 2 Requires infusion interruption but responds promptly to symptomatic treatment (e.g., antihistamines, NSAIDS, narcotics, IV fluids); prophylactic medications indicated for ≤ 24 hrs	
Stop Infusion and monitor symptoms.
 
Additional appropriate medical therapy may include but is not limited to:
 
 IV fluids Antihistamines NSAIDS Acetaminophen Narcotics 
Increase monitoring of vital signs as medically indicated until the subject is deemed medically stable in the opinion of the investigator.
 
If symptoms resolve within one hour of stopping drug infusion, the infusion may be restarted at 50% of the original infusion rate (e.g., from 100 mL/hr to 50 mL/hr). Otherwise, dosing will be held until symptoms resolve and the subject should be premedicated for the next scheduled dose.
 
Subjects who develop Grade 2 toxicity despite adequate premedication should be permanently discontinued from further trial treatment administration.
	
Subject may be premedicated 1.5h (\pm 30 minutes) prior to infusion of pembrolizumab (MK-3475) with:
 
 Diphenhydramine 50 mg po (or equivalent dose of antihistamine). Acetaminophen 500-1000 mg po (or equivalent dose of antipyretic).
Grades 3 or 4 Grade 3: Prolonged (i.e., not rapidly responsive to symptomatic medication and/or brief interruption of infusion); recurrence of symptoms following initial improvement; hospitalization indicated for other clinical sequelae (e.g., renal impairment, pulmonary infiltrates) Grade 4: Life-threatening; pressor or ventilatory support indicated	
Stop Infusion.
 
Additional appropriate medical therapy may include but is not limited to:
 
 IV fluids Antihistamines NSAIDS Acetaminophen Narcotics Oxygen Pressors Corticosteroids Epinephrine 
Increase monitoring of vital signs as medically indicated until the subject is deemed medically stable in the opinion of the investigator.
 
Hospitalization may be indicated.
 
Subject is permanently discontinued from further trial treatment administration.
	No subsequent dosing

Appropriate resuscitation equipment should be available in the room and a physician readily available during the period of drug administration.

5.7 Diet/Activity

5.7.1 Diet

Subjects should maintain a normal diet unless modifications are required to manage an AE such as diarrhea, nausea or vomiting.

5.7.2 Contraception

Pembrolizumab may have adverse effects on a fetus in utero. Furthermore, it is not known if pembrolizumab has transient adverse effects on the composition of sperm.

For this trial, male subjects will be considered to be of non-reproductive potential if they have azoospermia (whether due to having had a vasectomy or due to an underlying medical condition).

Female subjects will be considered of non-reproductive potential if they are either:

- (1) Post-menopausal (defined as at least 12 months with no menses without an alternative medical cause; in women < 45 years of age a high follicle stimulating hormone (FSH) level in the postmenopausal range may be used to confirm a post-menopausal state in women not using hormonal contraception or hormonal replacement therapy. In the absence of 12 months of amenorrhea, a single FSH measurement is insufficient.);
OR
- (2) have had a hysterectomy and/or bilateral oophorectomy, bilateral salpingectomy or bilateral tubal ligation/occlusion, at least 6 weeks prior to screening;
OR
- (3) has a congenital or acquired condition that prevents childbearing.

Female and male subjects of reproductive potential must agree to avoid becoming pregnant or impregnating a partner, respectively, while receiving study drug and for 120 days after the last dose of study drug by complying with one of the following:

- (1) use (or have their partner use) acceptable contraception during heterosexual activity.

Acceptable methods of contraception are‡:

Single method (one of the following is acceptable):

- intrauterine device (IUD)
- vasectomy of a female subject's male partner
- contraceptive rod implanted into the skin

Combination method (requires use of two of the following):

- diaphragm with spermicide (cannot be used in conjunction with cervical cap/spermicide)
- cervical cap with spermicide (nulliparous women only)
- contraceptive sponge (nulliparous women only)

- male condom or female condom (cannot be used together)
- hormonal contraceptive: oral contraceptive pill (estrogen/progestin pill or progestin-only pill), contraceptive skin patch, vaginal contraceptive ring, or subcutaneous contraceptive injection

Periodic abstinence (e.g., calendar, ovulation, sympto-thermal, post-ovulation methods, etc.) and withdrawal are not acceptable methods of contraception.

‡If a contraceptive method listed above is restricted by local regulations/guidelines, then it does not qualify as an acceptable method of contraception for subjects participating at sites in this country/region.

Subjects should be informed that taking the study medication may involve unknown risks to the fetus (unborn baby) if pregnancy were to occur during the study. In order to participate in the study subjects of childbearing potential must adhere to the contraception requirement (described above) from the day of study medication initiation (or 14 days prior to the initiation of study medication for oral contraception) throughout the study period up to 120 days after the last dose of trial therapy. If there is any question that a subject of childbearing potential will not reliably comply with the requirements for contraception, that subject should not be entered into the study.

5.7.3 Use in Pregnancy

If a subject inadvertently becomes pregnant while on treatment with pembrolizumab, the subject will immediately be removed from the study. The site will contact the subject at least monthly and document the subject's status until the pregnancy has been completed or terminated. The outcome of the pregnancy will be reported to the Sponsor and to Merck without delay and within 24 hours to the Sponsor and within 2 working days to Merck if the outcome is a serious adverse experience (e.g., death, abortion, congenital anomaly, or other disabling or life-threatening complication to the mother or newborn).

The study investigator will make every effort to obtain permission to follow the outcome of the pregnancy and report the condition of the fetus or newborn to the Sponsor. If a male subject impregnates his female partner the study personnel at the site must be informed immediately and the pregnancy reported to the Sponsor and to Merck and followed as described above and in Section 7.3.2.

5.7.4 Use in Nursing Women

It is unknown whether pembrolizumab is excreted in human milk. Since many drugs are excreted in human milk, and because of the potential for serious adverse reactions in the nursing infant, subjects who are breast-feeding are not eligible for enrollment.

5.8 Subject Withdrawal/Discontinuation Criteria

Subjects may withdraw consent at any time for any reason or be dropped from the trial at the discretion of the investigator should any untoward effect occur. In addition, a subject may be withdrawn by the investigator for any reason including the following: if enrollment into the trial

is inappropriate, the trial plan is violated, or for administrative and/or other safety reasons. Specific details regarding discontinuation or withdrawal are provided in Section 7.2.4 Other Procedures.

A subject must be discontinued from the trial treatment for any of the following reasons:

- The subject or legal representative (such as a parent or legal guardian) withdraws consent.
- Confirmed radiographic disease progression per irRECIST
Note: For unconfirmed radiographic disease progression, please see Section 5.8.1
Note: A subject may be granted an exception to continue on treatment with confirmed radiographic progression if clinically stable or clinically improved, please see Section 5.8.1
- Intercurrent illness that prevents further administration of treatment
- Unacceptable adverse events as described in Section 5.4.3
- Investigator's decision to withdraw the subject
- The subject has confirmed positive serum pregnancy test
- Completed 12 months of study therapy
- Administrative reasons

The End of Treatment and Follow-up visit procedures are listed in Section 6.0 (Protocol Flow Chart) and Section 7.2.5 (Visit Requirements). After the end of treatment, each subject will be followed for 30 days for adverse event monitoring (serious adverse events will be collected for 90 days after the end of treatment as described in Section 7.3.3.1). Subjects who discontinue for reasons other than progressive disease will have post-treatment follow-up for disease status until disease progression, initiating a non-study cancer treatment, withdrawing consent or becoming lost to follow-up. After documented disease progression each subject will be followed by telephone for overall survival until death, withdrawal of consent, or the end of the study, whichever occurs first.

5.8.1 Discontinuation of Study Therapy Due to Disease Progression

Immunotherapeutic agents such as pembrolizumab and IL-2 may produce antitumor effects by potentiating endogenous cancer-specific immune responses. The response patterns seen with such an approach may extend beyond the typical time course of responses seen with cytotoxic agents and can manifest as a clinical response after an initial increase in tumor burden or even the appearance of new lesions.

Immune related RECIST will be used for assessment of tumor response for the purposes of managing subjects on Protocol treatment and decision making for discontinuation of study therapy due to disease progression. PD should be confirmed no earlier than 4 weeks later according to the criteria outlined in Table 11 below. Subjects who are deemed clinically unstable or who have biopsy proven new metastatic lesions are not required to have repeat imaging for confirmation. This decision will be based on clinical judgment of a subject's overall clinical

condition, including performance status, clinical symptoms, and laboratory data. At a minimum, subjects must meet the following criteria for continued treatment on study after disease progression is identified at a tumor assessment:

When feasible, subjects should not be discontinued until progression is confirmed; however, the decision to continue study treatment after the first evidence of disease progression is at the investigator's discretion based on the clinical status of the subject.

Subjects may receive study treatment while waiting for confirmation of PD if they are clinically stable as defined by the following criteria:

- No decline in ECOG performance status.
- Absence of new or worsening symptoms.
- Absence of rapid progression of disease.
- Absence of progressive tumor at critical anatomical sites (e.g., spinal cord compression) requiring urgent alternative medical intervention.

Table 11. Imaging and Treatment after First Radiologic Evidence of Progressive Disease

	Clinically Stable		Clinically Unstable	
	Imaging	Treatment	Imaging	Treatment
First radiologic evidence of PD	Repeat imaging at \geq 4 weeks to confirm PD	May continue study treatment at the investigator's discretion while awaiting confirmatory scan	Repeat imaging at \geq 4 weeks to confirm PD if possible	Discontinue treatment
Repeat scan confirms PD	No additional imaging required	Discontinue treatment	No additional imaging required	N/A
Repeat scan shows SD, PR, or CR ⁱ	Continue regularly scheduled imaging assessments every 6 weeks x 3 then resume imaging every 12 weeks thereafter.	Continue study treatment at the investigator's discretion	Continue regularly scheduled imaging assessments every 6 weeks x 3 then resume imaging every 12 weeks thereafter.	May restart study treatment if condition has improved and/or clinically stable per investigator's discretion

ⁱ SD, PR, CR is based on new baseline from first evidence of PD.

5.8.2 Discontinuation of Study Therapy after CR

Discontinuation of treatment may be considered for subjects who have attained a confirmed CR that have been treated for at least 24 weeks with pembrolizumab and had at least two treatments with pembrolizumab beyond the date when the initial CR was declared. Subjects who then experience radiographic disease progression may be eligible for up to one year of additional treatment with pembrolizumab via the Second Course Phase at the discretion of the investigator if no cancer treatment was administered since the last dose of pembrolizumab, the subject meets the safety parameters listed in the Inclusion/Exclusion criteria, and the trial is open. Subjects will resume therapy at the same dose and schedule at the time of initial discontinuation. Additional details are provided in Section 5.4.

5.9 Subject Replacement Strategy

For the phase I component, any patient who is unevaluable for DLT will be replaced. For the phase II component, patients must have completed at least 3 of the planned 4 study injections to be considered evaluable.

5.10 Clinical Criteria for Early Trial Termination

Early trial termination will be the result of principal investigator discretion. The following criteria specified below:

1. Quality or quantity of data recording is inaccurate or incomplete
2. Poor adherence to protocol and regulatory requirements
3. Incidence or severity of adverse drug reaction in this or other studies indicates a potential health hazard to subjects
4. Plans to modify or discontinue the development of the study drug

In the event that no patients are able to tolerate the lowest dose of IL-2 (3×10^6 IU), the study will be terminated.

In the event the DSMC decides the study is not safe for patients, the study will be terminated.

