5.2 Trial Treatments

This is a phase I/II study that will evaluate the safety and toxicity of this combinatorial approach. Eligible patients ≥ 18 years of age with histologically proven advanced solid malignancy or lymphoma who have failed PD-1 / PD-L1 checkpoint blockade therapy will be enrolled. Patients must have a candidate treatment lesion accessible and safe for radiotherapy and serial intralesional injections as specified by the protocol. They must also have at least one target lesion (distinct from treatment lesion and outside of treatment lesion radiation field) evaluable for response by RECIST.

This study will consist of a phase I dose escalation / de-escalation using a standard 3+3 design to determine safety and MTD of intralesional IL-2 which will be dose escalated in conjunction with standard fixed doses of RT and Pembrolizumab. The study will begin at dose level 3 and the dose will be de-escalated if needed to determine the MTD. At the MTD there will be a phase II dose expansion which will incorporate a simon-two stage design to assess efficacy and safety.

Patients will receive pembrolizumab and intralesional IL-2 in combination with hypofractionated radiotherapy.

- Radiotherapy will be delivered to the treatment lesion during the second cycle of therapy using an 8 Gy x 3 fractions palliative regimen. Fractions may be delivered on consecutive days or every other day but must be completed during weeks 1-2 of cycle 2 and will not be repeated in future cycles.
- Pembrolizumab will be delivered at 200 mg in three-week cycles .

- A total of four interleukin-2 treatments will be delivered into the treatment lesion by intralesional injection biweekly (at least 48 hours apart) starting 24-96 hours after the completion of radiotherapy and to be completed during the second on-trial cycle of Pembrolizumab. Intralesional injections will be performed by direct visualization and/or palpation of the lesion or under ultrasound or CT guidance as indicated. Intralesional IL-2 injections will follow guidelines which we have previously published [46]. IL-2 will be administered at three dose levels: 1) 3×10^6 IU, 2) 7×10^6 , 3) 15×10^6 IU. The study will begin at dose level 3 and the dose will be de-escalated as needed to establish the MTD.

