At dose escalation levels 2 and 3 and in the phase II portion each patient will receive a test dose of 3×10^6 IU for their first injection prior to escalation to higher doses according to our published guidelines. For example, at dose level 3 each patient will receive an initial test dose of 3×10^6 IU of IL-2, which will be escalated to 7×10^6 for the second treatment and then 15×10^6 IU for the final two treatments as tolerated. If a dose level is not tolerated the treatment will be de-escalated to previous dose levels for subsequent treatments. If 3 million IU IL-2 is not tolerated the dose can be de-escalated to 1 million IU IL-2. If 1 million IU IL-2 is not tolerated the treatment will be deemed intolerable and patient removed from study (see Figure 6).

Patients will be assessed by a physician once during the first week of radiotherapy, weekly during intralesional IL-2 injections, and with every cycle of pembrolizumab. Routine laboratory evaluation will occur pre-treatment. For response assessment patient will have imaging pre-treatment and after every three cycles of Pembrolizumab. For collateral studies patients will undergo mandatory treatment lesion biopsies and blood draws pre-treatment and during the needle placement for the final IL-2 treatment.

Preliminary efficacy as determined by abscopal response rate, ORR, DCR and PFS will be assessed every 3 cycles. Patients on active treatment at 12 months may continue to receive pembrolizumab but will revert to standard of care (SOC) management and be labeled in “follow up”. At this time only PFS and long-term toxicity data will be collected every 3 months.

The primary endpoint is to determine if this regimen converts patients with resistance to PD-1/PD-L1 checkpoint blockade into responders as determined by abscopal response rate (defined as response rate at lesions not treated with RT + IL-2) using irRECIST as well as ORR, DCR, and PFS using RECIST 1.1. The secondary endpoint is tolerability, safety, and toxicity using CTCAE v4.03. Correlative studies include immunophenotyping serial tumor biopsies and blood samples.

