5.4 Dose Selection/Modification

5.4.1 Intralesional IL-2

5.4.1.1 Maximum Tolerated Dose Selection

In Phase I, four target doses of intralesional IL-2 will be evaluated:

- Dose Level -1: 1×10^6 IU;
- Dose Level 1: 3×10^6 IU;
- Dose Level 2: 7×10^6 IU;
- Dose Level 3: 15×10^6 IU (starting dose)

We will initiate the trial at Dose level 3 and de-escalate to lower dose levels as needed to establish the MTD. If dose level -1 is not tolerated the study will be halted and modified after discussion with principal investigators and study sponsors.

The MTD will be defined in phase I as the highest dose at which no more than one of six patients develops a DLT or Dose Level 3 if the MTD is not reached. A DLT is defined as one of the following which occurs during DLT period which lasts until 7 days after last injection of IL-2:

- grade ≥ 4 injection site reaction OR
- grade ≥ 3 treatment related immunologic adverse event (excluding injection site reactions) OR
- other grade ≥ 3 treatment related adverse events that do not resolve to grade ≤ 2 within 14 days OR
- AST/ALT $> 3 \times$ ULN with bilirubin $> 2 \times$ ULN, OR
- pneumonitis that requires holding treatment > 14 days

Table 4 and

Table 5 describe the standard dosing rules that will be followed. At dose levels 2 and 3 each patient will receive a test dose of 3×10^6 IU for their first injection prior to escalation to higher doses according to our published guidelines. For example, at dose level 3 each patient will receive an initial test dose of 3×10^6 IU of IL-2, which will be escalated to 7×10^6 for the second treatment and then 15×10^6 IU for the final two treatments as tolerated. If a dose level is not tolerated the treatment will be de-escalated to previous dose levels for subsequent treatments. Subjects who are not evaluable for toxicity will be replaced for DLT assessment. If subjects cannot receive 75% of intended dose of study treatment, for reasons other than toxicity and did not experience a DLT, they will be replaced for DLT assessment.

Table 4. Phase I Dose Escalation and De-Escalation Rules

[figure not shown]
Number of Patients with DLT at a Given Dose Level	Escalation Decision Rule
0 out of 3	Enter 3 additional patients at the next dose level.
1 out of 3	Enter 3 additional patients at the dose level. If no additional DLT enter 3 additional patients at the next dose level.
2 out of 3 or 6	De-escalate the dose to the next lower level and accme 3 patients.

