Phase II will be conducted using the MTD. For phase II, a treatment limiting toxicity (TLT) will be defined as an IL-2 treatment related grade 3-4 non-hematologic or grade 4 hematologic toxicity and will require dose de-escalation. A TLT must resolve to grade 2 or less before the next de-escalated dose is administered. Treatment intolerance will be measured in phase II to define the percentage of patients that have to come off study treatment or miss an IL-2 treatment due to inability to tolerate the full course of therapy. This is a separate measure from the MTD assessment in phase I and is only measured during phase II. Treatment intolerance will be defined as a TLT that does not resolve to grade 2 or less within 5 days, is not responsive to management, or occurs at the lowest dose level (1 million IU IL-2). In this case the patient will be removed from trial and the therapy will be deemed intolerable for that patient. If a dose of IL-2 is missed due to TLT not resolving to grade 2 or less within 5 days this falls into the definition of treatment intolerance. If a dose IL-2 is missed for other reasons this does not qualify as treatment intolerance. The TLT period begins with the administration of IL-2 and lasts up to 7 days after the last injection of IL-2. As outlined above the initial dose of intralesional IL-2 will be administered as 3 million IU test dose. If there are IL-2 related grade 3-4 non-hematologic or grade 4 hematologic treatment related adverse effects the dose will be de-escalated for the second treatment to 1 million IU. If there are grade 3-4 non-hematologic adverse effects, or grade 4 hematologic adverse effects at the 1 million IU dose the patient will be removed from study and the therapy deemed intolerable. For a given patient dose escalation will occur if there are no IL-2 related grade 3-4 non-hematologic or grade 4 hematologic treatment related toxicities. For each patient if a dose level is associated with grade 3-4 non-hematologic or grade 4 hematologic toxicity this will be deemed a TLT and the patient will be de-escalated to the lower dose for the next treatment. Once the dose is decreased there will be no further dose re-escalation allowed for an individual patient. If a planned dose cannot be delivered within the prescribed week it will be skipped.

Intratumoral IL-2 is well tolerated per Table 1 above with the majority of patients experiencing mild toxicity.

Table 7. Adverse Event Management

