9.3 Safety

The adverse events observed will be summarized as frequency, proportion of patients, and exact 95% confidence interval for proportion, categorized by type (organ affected or laboratory determination), severity by CTCAE v4.03 and nadir or maximum values for the laboratory measures), time of onset (i.e., course number), duration, and reversibility or outcome. Tables will be created to summarize these toxicities by dose and course. The secondary endpoint is safety and toxicity. A treatment limiting toxicity (TLT) will be defined as a treatment related grade 3-4 non-hematologic toxicity and will require dose de-escalation. If a TLT does not resolve within 5 days, is not responsive to management, or occurs at the lowest dose level (1 million IU IL-2) after de-escalation then that patient will be removed from trial and the therapy will be deemed intolerable. Therapy will be deemed safe and tolerable if no greater than 33% of patients find the treatment intolerable.

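### Section 5.10 ties study termination to a lowest IL-2 dose of 3×10^6 IU, but the protocol's lowest dose is 1×10^6 IU (minor; rare trigger)

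*Combined protocol and SAP*

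**What the plan says.** Section 5.10 lists grounds for early termination. One sentence is tied to dose. It begins "In the event that no patients are able to tolerate the lowest dose of IL-2", states the dose in parentheses as 3×10^6 IU, and says the study will be terminated.

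Elsewhere the lowest dose is 1×10^6 IU:

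- Section 5.4.1.1 states "In Phase I, four target doses of intralesional IL-2 will be evaluated" and lists Dose Level -1 at 1×10^6 IU, below Levels 1, 2 and 3 at 3, 7 and 15×10^6 IU. The Section 2.0 table, Section 4.8.5 and Table 5 agree. Table 6 has the corresponding Phase II step.
- Section 9.3 speaks of a toxicity that "occurs at the lowest dose level (1 million IU IL-2) after de-escalation". Sections 5.2.2.3 and 5.4.1.2 also name 1 million IU as the lowest level.

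Dose finding starts at Level 3 and moves down. With 2 DLTs out of 3 or 6 patients, Table 4 says "De-escalate the dose to the next lower level". The end of that path is in Section 5.4.1.1: "If dose level -1 is not tolerated the study will be halted and modified after discussion with principal investigators and study sponsors".

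Within a patient, Section 5.2 says "If 3 million IU IL-2 is not tolerated the dose can be de-escalated to 1 million IU IL-2". For Phase II, Section 5.4.1.2 says that after a qualifying toxicity on the test dose "the dose will be de-escalated for the second treatment to 1 million IU".

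**The concern.** A stopping rule has to name the dose at which it acts. In Section 5.10 the label (lowest dose) and the number (3×10^6 IU) do not belong together, because a lower level exists and is the planned fallback. If no patient tolerated 3×10^6 IU, the study team would hold two written instructions: close the study, or continue down the dose ladder. Obeying one means departing from the other. Read literally, Section 5.10 would close the study before Level -1 had been tried as a cohort dose, in the very situation that level is there for.

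The outcomes also differ in kind. Section 5.10 terminates; Section 5.4.1.1 halts the study for discussion and modification.

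**Working it through.** **1. Which dose is lowest?** Section 5.4.1.1 and Table 5 list 1, 3, 7 and 15×10^6 IU, so the minimum is 1×10^6 IU. The figure in Section 5.10 is reproduced only if Level -1 is left out: the minimum of 3, 7 and 15 is 3×10^6 IU. Section 5.2 does count that way ("IL-2 will be administered at three dose levels"), and Section 9.1 also speaks of three escalation levels. That may be where the number came from, but the documents do not say so. It does not settle the matter, since Section 5.2 itself goes on to allow 1 million IU.

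**2. What each section orders.** Table 5 gives 3×10^6 IU as the first injection at Levels 1, 2 and 3. For this comparison, assume that failing to tolerate that injection counts as a DLT.

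| Situation | Section 5.10 dose sentence | Table 4 and Section 5.4.1.1 |
|---|---|---|
| All patients fail 3×10^6 IU at Level 3 | Terminate | Go to Level 2 |
| All patients fail 3×10^6 IU at Level 2 | Terminate | Go to Level 1 |
| All patients fail 3×10^6 IU at Level 1 | Terminate | Go to Level -1 |
| Level -1 not tolerated | Not addressed | Halt and modify |

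The direct choice between ending the study and trying Level -1 arises in the third row only. In the first two rows the 5.10 trigger could be met on the first injection, but Table 4 leads to a level that again starts at 3×10^6 IU.

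**3. How likely is the trigger?** The documents give no failure rate for 3×10^6 IU in this combination, so p below is an assumption. With n patients who fail independently, each with probability p,

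P(all n fail) = p^n.

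| p | n = 3 | n = 6 | n = 9 |
|---|---|---|---|
| 10% | 0.10^3 = 0.001 | – | – |
| 20% | 0.20^3 = 0.008 | – | – |
| 33% | 0.33^3 = 0.036 | 0.33^6 = 0.0013 | 0.33^9 = 0.00005 |
| 50% | 0.50^3 = 0.125 | 0.50^6 = 0.016 | 0.50^9 = 0.002 |

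The columns for 6 and 9 are shown because Section 5.10 does not say whether it counts one cohort or everyone treated so far. Section 4.8.4 reports grade 3 toxicity in 2 of 187 patients across earlier intralesional IL-2 trials. With p = 2/187 = 0.0107, p^3 = 1.2×10^-6, about one in a million. Those trials used other regimens, so this figure is only indicative.

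**The case against.** The strongest reply is that this is a wrong parenthesis with almost no practical reach. The two rules have different triggers: Table 4 acts on 2 DLTs out of 3 or 6, whereas Section 5.10 needs every patient to fail and does not define tolerance there. By the time all three patients at Level 1 had failed, Table 4 would already have called for Level -1. Any error would stop the study too early, not too late. Section 5.10 also opens by placing early termination in the principal investigator's discretion.

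Most of this stands. It limits the point to a minor correction, and the higher probabilities in the table need failure rates of 33% to 50% that nothing in the documents supports. The appeal to discretion does not cure the mismatch, because the disputed sentence is worded as a firm consequence. The difference in triggers makes a collision rarer, but when Level 1 fails in every patient both sections apply and disagree.

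A reader might infer that the choice between termination and Level -1 arises at any of Levels 1 to 3, since each begins with 3×10^6 IU. Table 4 does not support that: it moves one level at a time, so only Level 1 leads directly to Level -1.

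**Conclusion.** Section 5.10 is wrong as written: the dose it calls lowest is not the lowest in the protocol. The direct conflict is confined to Dose Level 1. There Section 5.10 terminates, while Table 4 and Section 5.4.1.1 send the study to Level -1 and halt it only if that level is not tolerated. The difference between terminating and halting to modify also needs resolving.

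The size is small. On the independence assumption, a cohort of three all failing has probability 0.001 to 0.125 for assumed failure rates of 10% to 50%, and far less at the indicative historical rate. A reader might infer that the error weakens the efficacy design; it does not. The sentence concerns dose-finding conduct and stopping, and sample size, alpha and power do not depend on it. The finding that the number is wrong rests on comparing the sections, not on the probabilities.

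**What to change.** Replace the dose sentence in Section 5.10 with: *If Dose Level -1 (1×10^6 IU) is not tolerated in Phase I, the study will be halted as described in Section 5.4.1.1.* The sponsor should confirm whether the intended consequence is to halt and modify or to terminate, and use the same word in both sections.

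Changing only the number in the present sentence would not be enough. In Phase II, 1×10^6 IU is given only after a treatment limiting toxicity. If a single reduced patient then failed it, no patient given that dose would have tolerated it, and the sentence could literally end the trial. Section 5.4.1.2 removes only that patient, and the new wording should leave such patients to that section.

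The other criteria in Section 5.10 and its DSMC sentence stay as they are. The cost is one sentence in an amendment, plus a matching word in Section 5.4.1.1 if the sponsor chooses termination. No extra patients or data are needed.
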